9.1 General

In the case that adverse events related to the study intervention are reported, these will be recorded per the descriptions and grading scales found in the revised National Cancer Institute Common Terminology Criteria for Adverse Events (CTCAE) Version 4.0 for adverse event reporting that can be found at <http://ctep.cancer.gov/reporting/ctc.html>.

Information about all intervention-related adverse events, including those volunteered by the subject, discovered by investigator/study personnel questioning, or detected through physical examination, or other means, will be collected, followed, and reported appropriately.

The adverse events related to any ongoing treatment for the patient's underlying cancer or other medical conditions will not be collected.

9.2 Reporting Procedures

All intervention-related adverse events will be captured on the appropriate study-specific report forms (CRFs) or in a designated database.

The same applies to any adverse event classified as a "serious adverse event;" these will also only be reported if intervention-/study-related.

Any unexpected intervention-related adverse events and serious adverse events will be reported to the IRB per current institutional standards. If an adverse event requires modification of the informed consent, these modifications will be provided to the IRB with the report of the adverse event. If an adverse event requires modification to the study protocol, these modifications will be provided to the IRB as soon as is possible.

10. Measurement of Effect

The primary outcome is described Section 13.1 below.

For any outcome other than a patient-reported outcome, such as diary entries, the data will be recorded or reviewed by the study coordinator, not the treatment person.

Our statistical consultation service is headed by [name], Professor of Oncology and Director of the Quantitative Sciences Program and Biostatistics/ Bioinformatics Division. He will appoint a masters-level statistician to continue work with us as data become available.

11. Data and Safety Monitoring

11.1 Data Management

All information will be collected on study-specific case report forms by the study staff or in a designated database.

All study data will be reviewed for completeness and accuracy by the Principal Investigator. The study data may also be periodically reviewed by the Sidney Kimmel Comprehensive Cancer Center Clinical Research Office.

11.2 Monitoring

This is a Level 1 study under the SKCCC Data Safety Monitoring Plan (06/25/2010). The Clinical Research Office QA Group will perform an audit at the end of the first year and then periodically depending on the rate of accrual and prior audit results.

The SKCCC CRO will perform data and safety monitoring, oversight of adverse events and other protocol events for this research.

All trial monitoring and reporting will be reviewed annually by the SKCCC Safety and Monitoring Committee.

12. Administrative Procedures

12.1 Protocol Amendments

Any changes to the protocol will be made in the form of an amendment and must be approved by the IRB before implementation. The Principal Investigator (or her designee) is responsible for the coordination and development of all protocol amendments, and will disseminate this information to the participating centers.

12.2 Informed Consent

The Principal Investigator (or his designee) will explain to each subject the nature of the study, its purpose, procedures involved, expected duration, potential risks and benefits. Each subject will be informed that participation in the study is voluntary and that she may withdraw from the study at any time, and that withdrawal of consent will not affect her subsequent medical treatment. This informed consent will be given by means of a standard written statement and will be submitted for IRB approval prior to use. No patient will enter the study before her informed consent has been obtained. In accordance with the Health Insurance Portability and Accountability Act (HIPAA), the written informed consent document (or a separate document to be given in conjunction with the consent document) will include a subject authorization to release medical information to the study sponsor and supporting agencies and/or allow these bodies, a regulatory authority, or Institutional Review Board access to subjects' medical information that includes all hospital records relevant to the study, including subjects' medical history.

12.3 Ethics and Good Clinical Practice

This study must be carried out in compliance with the protocol and Good Clinical Practice, as described in:

1. ICH Harmonized Tripartite Guidelines for Good Clinical Practice 1996.
2. US 21 Code of Federal Regulations dealing with clinical studies (including parts 50 and 56 concerning informed consent and IRB regulations).
3. Declaration of Helsinki, concerning medical research in humans (Recommendations Guiding Physicians in Biomedical Research Involving Human Subjects, Helsinki 1964, amended Tokyo 1975, Venice 1983, Hong Kong 1989, Somerset West 1996).

The investigator agrees to adhere to the instructions and procedures described in it and thereby to adhere to the principles of Good Clinical Practice.

12.4 Regulatory Authorities

12.4.1 Institutional Review Board

Information regarding study conduct and progress will be reported to the Institutional Review Board (IRB) per the current institutional standards of each participating center.

13. Statistical Considerations

13.1 Overall

The primary endpoint is change in patient-reported pain from day 0 to day 28 as measured by the Modified Brief Pain Index, question #3 (Appendix B). This endpoint also serves to get preliminary information for planning future, larger, phase III studies.

Secondary endpoints will include the total Brief Pain Inventory score, the sensory and motor subscales of the CIPN 20, and the Morphine Oral Equivalents Dose at day 28 compared to sham therapy. We will also report the daily (days 1-10) changes in “pain now” before and after each treatment, to be comparable to all the other reported studies.

13.2 Sample Size and Accrual

We are anticipating that the starting pain score will be 4-6 based on VCU, Italian, and Mayo Clinic data. We are anticipating that the reduction in CIPN pain score will be over 50% based on the VCU, Italian, and Mayo Clinic data. We anticipate a possible 10% reduction in pain scores over 30 days based on the randomized trial data for placebo compared to gabapentin and other drugs.

The primary objective of this study is to determine if patients randomized to the Scrambler therapy have a larger reduction in pain scores than those randomized to the placebo, or sham, treatment. Power calculations were performed using a simulation approach. Pain scores were simulated using a bivariate normal distribution with a mean (SD) of 4 (2) at baseline for both groups, with means ranging from 2.8 to 3.6 (30% to 10% decrease) for the control group post-treatment and mean of 2 (50% decrease) for the Scrambler group post-treatment. Post-treatment scores for both treatment arms were assumed to have a SD = 1.5. Based on previous data, a value of 0.3 was assumed for the within-patient correlation between pre- and post-treatment scores.

Any patient with 1) a simulated pain score at baseline less than 4, or 2) a simulated pain score less than 0 post-treatment, or 3) a simulated pain score greater than 10 at either time point, was replaced until all criteria were met, to reflect the actual scores we will see. Simulated scores were then rounded to the nearest integer to also reflect the nature of the scale. The change in pain score was calculated for each patient, and differences were compared between groups with a two-sample t test. Power was defined as the proportion of simulations that yielded a one-sided p value for the t test < 0.10 . 1000 simulations for each scenario were performed. The table below shows sample sizes and resulting power for the differences between treatment arms.

Total N	Power	Percent Decrease in Treatment Arm	Percent Decrease in Control Arm
30	87.3%	50%	10%
60	86.6%	50%	20%
90	77.6%	50%	30%

To detect the proposed effect size, 30 patients total, 15 on Scrambler therapy and 15 on the sham arm, will yield 87.3% power with a 1-sided type I error rate of 10%.

We will record the same pain data on the group that receives sham treatment if they elect to receive actual Scrambler treatment at the end of their 28-day treatment period. However, this is not a “crossover” design trial wherein each patient serves as his/her own control. Data collection for the primary endpoint will occur before patients in the sham arm are given the option to receive Scrambler treatment. This data will not be formally analyzed but instead used to help plan future studies.

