The primary endpoint is patient reported change in pain from day 0 to day 28, on a numeric scale of 0-10 (question #3 of the Modified Brief Pain Inventory, Appendix B). Secondary endpoints will include changes in the complete Brief Pain Inventory, the CIPN EORTC Q-20 scale, and changes in pain drug use. With 30 patients and a one-sided type I error rate of 10%, we have 87% power to detect a 50% reduction in pain observed in single arm trials and a 10% reduction in pain with sham treatment, in patients with a starting pain score of ≥ 4 .

Subjects enter the study and get scrambler therapy or placebo for 10 sessions, usually as weekdays, for 2 weeks. Then, they are followed without any protocol treatment until Day 28 when the primary endpoint is assessed. After the primary assessment is done the groups are “un-blinded” and informed of their study treatment, real or sham. Those in the sham group with scores ≥ 4 will be offered the standard 10 scrambler sessions. All patients are followed for a total of 3 months.

2. Schema

3. Objectives

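### The 87% power is stated for a 50% v 10% fall in patients scoring 4 or more, but the simulated patients scoring 4 or more fall 55% v 29%: a labelling error in the conservative direction

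*Combined protocol and SAP*

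**What the plan says.** Section 1 claims that 30 patients, tested one-sided at 10%, give "87% power to detect a 50% reduction in pain observed in single arm trials and a 10% reduction in pain with sham treatment", and names the population: "in patients with a starting pain score of ≥ 4". That is also the eligible population (criterion 6.1.5).

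Section 13.2 gives the simulation behind the claim. Scores are bivariate normal, with baseline mean 4 (SD 2) in both arms, post-treatment SD 1.5 and pre/post correlation 0.3. The Scrambler post-treatment mean is 2, and sham is simulated "with means ranging from 2.8 to 3.6 (30% to 10% decrease) for the control group post-treatment". Screening comes afterwards: "Any patient with 1) a simulated pain score at baseline less than 4", or with a post-treatment score below 0, or with either score above 10, is redrawn. Scores are then rounded, and change scores are compared with a two-sample t test: "Power was defined as the proportion of simulations that yielded a one-sided p value for the t test < 0.10".

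The table reports 87.3% (N=30, 50% v 10%), 86.6% (N=60, 50% v 20%) and 77.6% (N=90, 50% v 30%), and the section concludes: "To detect the proposed effect size, 30 patients total, 15 on Scrambler therapy and 15 on the sham arm, will yield 87.3% power". The sham assumption is introduced with "We anticipate a possible 10% reduction in pain scores over 30 days", citing placebo arms of drug trials.

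**The concern.** The percentages are fractions of the unscreened mean of 4 (2.0/4 and 3.6/4), but power is computed only in patients whose baseline is at least 4. The cut raises the baseline mean well above 4. With a correlation of only 0.3, the post-treatment means barely follow, so regression to the mean is added to the fall in both arms. The percentages in the table and in Section 1 then no longer describe the patients who generated the power.

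This matters because sham response is the main unknown in a sham-device trial. Read literally, the table says that N=30 is adequate only if sham patients improve by no more than 10%, and that a 20% sham fall calls for 60 patients. A sham fall near 29% in the actual trial would look like a failed planning assumption when it is what was simulated. The protocol also says that the trial is meant to inform the planning of larger studies, where the same table would be misleading.

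**Working it through.** **Inputs** (all from Section 13.2): baseline N(4, 2²); post-treatment SD 1.5; correlation 0.3; unscreened post-treatment means 2.0 (Scrambler) and 3.6 / 3.2 / 2.8 (sham); redraw if baseline <4, post <0 or either >10; round to integers; pooled two-sample t test on change, one-sided 0.10; 15, 30 or 45 per arm.

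**Step 1: reproduce the stated power.** With 60,000 trials per row:

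| N | Stated | Re-run | Gap in SEs of a 1000-run simulation |
|---|---|---|---|
| 30 | 87.3% | 85.2% | 1.9 |
| 60 | 86.6% | 87.7% | −1.1 |
| 90 | 77.6% | 75.4% | 1.6 |

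For the first row the SE is √(0.852 × 0.148 / 1000) = 1.1 points, and (87.3 − 85.2)/1.1 ≈ 1.9. The stated figures are therefore compatible with the described algorithm. Without the screening and rounding, the N=30 row gives only 77.5%, so the stated power does come from the screened patients.

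**Step 2: what the cut does, in closed form.** For a standard normal Z kept between 0 and 3 (baseline 4 to 10), E(Z) = [φ(0) − φ(3)] / [Φ(3) − 0.5] = (0.3989 − 0.0044)/0.4987 = 0.791.

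- Baseline mean: 4 + 2 × 0.791 = 5.58.
- Post-treatment mean, before the floor at 0: unscreened mean + 0.3 × 1.5 × 0.791 = unscreened mean + 0.36.
- Sham with no change in the unscreened mean: 4.36, a fall of 1 − 4.36/5.58 = 22.0% (21.6% simulated, with floor and rounding).

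Baseline therefore rises by 1.58 points and the post-treatment mean by only 0.36.

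**Step 3: realised means after all redraws and rounding** (4 million patients per arm):

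| Arm | Label | Baseline | Post | Mean fall | Realised % fall | Difference from Scrambler |
|---|---|---|---|---|---|---|
| Scrambler | 50% | 5.59 | 2.52 | 3.07 | 54.9% | – |
| Sham, N=30 | 10% | 5.57 | 3.97 | 1.60 | 28.7% | 1.47 |
| Sham, N=60 | 20% | 5.57 | 3.58 | 1.98 | 35.6% | 1.09 |
| Sham, N=90 | 30% | 5.57 | 3.21 | 2.36 | 42.4% | 0.71 |

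Cross-check: with a difference of 1.47, a change SD of about 1.71 and 15 per arm, the noncentrality is 1.47/(1.71 × √(2/15)) = 2.35, and noncentral-t power is 85.0%, matching Step 1.

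**Step 4: power for the contrast that Section 1 names.** The unscreened post-treatment means that yield falls of 50 / 10 / 20 / 30% in screened patients are 2.33 / 4.65 / 4.09 / 3.53. A 10% sham fall thus requires the unscreened sham mean to rise from 4 to 4.65.

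| True fall in eligible patients | Difference | N | Power |
|---|---|---|---|
| 50% v 10% | 2.23 | 30 | 98.6% |
| 50% v 20% | 1.67 | 30 | 90.8% |
| 50% v 20% | 1.67 | 60 | 99.3% |
| 50% v 30% | 1.12 | 90 | 96.3% |

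**Step 5: sensitivity to the SD.** The simulated change SD in screened patients is about 1.7. For the 2.23-point difference at 15 per arm, noncentral-t power is 95.8% at SD 2.0, 94.1% at 2.11 (the unscreened value, √(4 + 2.25 − 2 × 0.3 × 2 × 1.5)) and 86.9% at 2.5. The values 2.0 and 2.5 are assumptions, not figures from the documents.

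**The case against.** Four points can be made in the plan's favour.

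- **The inputs are disclosed and the quoted labels are correct against a mean of 4.** This stands for Section 13.2: 3.6/4 is a 10% decrease, and the screening is described. But the section never reports the realised means or falls, and Section 1 drops the unscreened reference and assigns the percentages to patients at 4 or more. Disclosure in one section does not make the other true.
- **The test is on points, not percentages.** The inputs imply 3.6 − 2.0 = 1.6 points and the simulation realises 1.47, the loss coming mainly from the floor at 0. Regression to the mean largely cancels between arms. This also stands, and it is why the stated power is right for what was simulated. The plan nevertheless states its effect in percentages, and 50% v 10% at the simulated baseline is 2.23 points.
- **The labels roughly fit at the entry threshold.** Simulated patients with a rounded baseline of 4 fall 43% v 8%. The fit is lost higher up: sham falls are 23% at baseline 5 and 33% at 6, within the 4–6 range that the plan anticipates.
- **The 98.6% is conditional, and nothing in the design changes.** Both are true. The figure relies on the plan's SD and correlation, and near-certain power should not be advertised for a 15-per-arm pilot without an SD sensitivity.

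**Conclusion.** The point holds. As written, Section 1 attaches 87% power to a contrast for which it was not computed, and the table headings in Section 13.2 invite the same reading. In the simulated eligible patients the contrast is 55% v 29% (1.47 points). The Scrambler figure is close to its label and fits the plan's expectation of a fall above 50%; the sham figure is nearly three times its label.

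The error is conservative under the plan's own SD and correlation: the named contrast would have about 98.6% power, and power would drop to the stated level only if the change SD were about 2.5 rather than the simulated 1.7. The adequacy of N=30 is not overturned, and the three tabulated powers are not claimed to be wrong for the simulated scenarios. It should be corrected because it misstates how much sham improvement the design tolerates: the plan's own simulation gives about 85% power with a sham fall of about 29%.

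**What to change.** Keep N=30, the one-sided t test and the 10% error rate. Then do one of the following.

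(a) **Relabel.** In the table and in Section 1, give the falls and point differences in screened patients (55% v 29%, 1.47 points; 55% v 36%, 1.09; 55% v 42%, 0.71) with the baseline mean of about 5.6, and note that the existing percentages refer to means before screening.

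(b) **Re-run.** Define the post-treatment means in the population with baseline 4 or more, so that the falls there are 50% v 10%, 20% and 30%. Use at least 10,000 replicates, replace the three powers and the Section 1 sentence, and show power over a range of change SDs.

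The choice depends on whether the anticipated 10% placebo fall already includes regression to the mean after an entry cut. The documents do not say, and the plan should: if it does, (b) is the consistent choice; if not, (a).

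The cost is a relabelled table or a short simulation, and one reworded sentence in each of Sections 1 and 13.2.

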13.3 Analysis Plan

13.3.1 Primary Endpoint

Pain scores will be summarized for each treatment arm at each time point with summary statistics. The mean change in scores in each treatment arm will be described with one sample paired t tests. The primary endpoint will be evaluated by testing for differences in change in pain scores between the two treatment arms with a one-sided t test. We will conclude a significant difference between treatment arms if the p value < 0.10. This difference will be reported with a 90% confidence interval.

Because this is a small study that is looking for an unbiased signal of activity, and the first randomized sham-controlled study for Scrambler therapy, we did not want to set the bar too high for concluding a positive effect of the treatment. This is not the definitive phase 3 studies for this treatment but more like an early randomized phase 2 study. Instead, this study will contribute information that will be useful in planning larger studies of the potential benefit of Scrambler therapy. The estimates used in the power calculation were based on data collected from a large series of patients, and even if we see the same differences in our study, we are less likely to conclude a positive treatment effect with a significance level < 0.05 due to the smaller sample size. We chose a type I error threshold of 10% to account for this, so that a p-value of 0.07 or 0.08 for the primary endpoint, for example, would not yield a negative study but instead suggest that larger studies are worthy of pursuit.

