13.3.2 Secondary Endpoints

Secondary endpoints include change in all of the pain scores (worst, least, average, right now, relief) recorded by the BPI, changes in the CIPN-20 sensory and motor subscales, and change in medication use and doses; all were measured at entry, 1, 2, and 3 months. All of these measurements will be summarized by treatment group using descriptive statistics and confidence intervals and tested for differences between treatment arms using t tests, Wilcoxon rank sum tests or Fisher’s exact tests as appropriate. Changes in scores over time will be analysed using appropriate regression models estimated with GEE or random effects to control for correlation between measurements from the same patient. All p values will be calculated for descriptive purposes only and we do not plan to control for multiple comparisons.

We will also compare baseline characteristics between treatment arms. Because treatment assignment is randomized, we do not expect to see differences. However, if we detect imbalance in variables such as concomitant medicinal use and supportive treatment, then we will control for this in the main analyses.

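### Does the 90% confidence interval for the primary difference have to be re-specified because the primary test is one-sided at 10%?

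*Combined protocol and SAP*

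**What the plan says.** Section 13.3.1 (Primary Endpoint) evaluates the primary endpoint by "testing for differences in change in pain scores between the two treatment arms with a one-sided t test". The decision rule follows directly: "We will conclude a significant difference between treatment arms if the p value < 0.10". The next sentence is the one at issue: "This difference will be reported with a 90% confidence interval". Neither the sidedness of the interval nor its relation to the test is stated.

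The same section explains the lenient threshold. It was chosen "so that a p-value of 0.07 or 0.08 for the primary endpoint, for example, would not yield a negative study"; such a result would instead point towards larger studies.

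Section 13.2 (Sample Size and Accrual) confirms that the 10% is one-sided: 15 patients per arm "will yield 87.3% power with a 1-sided type I error rate of 10" per cent. Section 13.3.2 (Secondary Endpoints) mentions intervals once more, summarising the measurements "using descriptive statistics and confidence intervals", with neither level nor sidedness. The document therefore does not settle which kind of 90% interval is meant.

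**The concern.** A one-sided test at 10% is matched by a one-sided 90% confidence bound, which is also the lower limit of a two-sided 80% interval. A two-sided 90% interval leaves 5% in each tail and so matches a one-sided 5% test. Most readers take a confidence interval with no further label as two-sided. On that reading, the test and the interval apply different standards to the same difference.

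The gap falls on the plan's own example. A p value of 0.07 or 0.08 is meant to count as encouraging, yet the two-sided 90% interval printed beside it would include zero. A reader could take the interval as contradicting the stated conclusion. What is at stake is how the primary result is read, in a trial whose declared purpose includes informing later studies.

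**Working it through.** **Inputs.** From 13.3.1: one-sided t test, threshold p < 0.10, example p values 0.07 and 0.08. From 13.2: 15 + 15 patients, so 28 degrees of freedom; baseline mean 4 (SD 2); post-treatment means 2.0 (Scrambler) and 3.6 (sham), both with SD 1.5; correlation 0.3; patients replaced if baseline is below 4, post-treatment below 0, or either score above 10; scores rounded to integers.

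**Step 1: the plan's power.** Re-running this simulation with 40,000 trials gives 85.4% power at one-sided p < 0.10, against 87.3% stated. The plan used 1000 simulations, with a Monte Carlo standard error of √(0.854 × 0.146 / 1000) = 1.1 points, so the two figures are compatible. Counting only one-sided p < 0.05 gives 74.8%. The stated power therefore belongs to the one-sided 10% rule.

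**Step 2: critical values.**
- Test at one-sided 10%: t(0.90; 28) = 1.3125.
- Two-sided 90% interval excludes zero only if t exceeds t(0.95; 28) = 1.7011.

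Any t between 1.3125 and 1.7011 is significant by the rule and has a two-sided 90% interval that includes zero.

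**Step 3: the plan's example.** In standard-error (SE) units the lower limit is t minus the critical value.

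| One-sided p | t | Two-sided 90% lower limit | One-sided 90% bound |
|---|---|---|---|
| 0.07 | 1.5189 | 1.5189 - 1.7011 = -0.182 | 1.5189 - 1.3125 = +0.206 |
| 0.08 | 1.4434 | 1.4434 - 1.7011 = -0.258 | 1.4434 - 1.3125 = +0.131 |

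The example p values are read as one-sided because the only primary test is one-sided. Read as two-sided, they would be one-sided 0.035 and 0.04, and the two-sided 90% interval would exclude zero; the text does not support that reading.

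**Step 4: in pain points.** The plan states no SD of change. The simulated SDs are 1.744 (sham) and 1.677 (Scrambler), pooled √((1.744² + 1.677²)/2) = 1.71, so SE = 1.71 × √(2/15) = 0.624.
- p = 0.07: difference 1.5189 × 0.624 = 0.95; two-sided 90% interval -0.11 to 2.01.
- p = 0.08: difference 1.4434 × 0.624 = 0.90; two-sided 90% interval -0.16 to 1.96.

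With the SD implied by the inputs before truncation, √(4 + 2.25 - 2 × 0.3 × 2 × 1.5) = 2.11, the SE is 0.770 and the intervals are -0.14 to 2.48 and -0.20 to 2.42.

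**Step 5: how often.** In the planning scenario, 85.4% - 74.8% = 10.6% of trials fall in the zone, which is 10.6/85.4, about 12.5%, of positive trials. A separate run of 100,000 trials gave 10.8% and 12.7%. With no effect the share is 10% - 5% = 5% of trials, half of all positive ones.

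**Step 6: what the interval controls.** Set beside the decision rule, the interval sentence only says how the difference is reported. The document does not use the interval to judge success, and does not present it as the inversion of the test. Changing its sidedness alters none of the test statistic, the p value, the 10% error rate, the power or the point estimate.

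**The case for a change.** The best case for amending the plan is that the interval is a main product of a trial meant to guide larger studies, that the mismatch falls exactly on the p values the plan uses as its example, and that one sentence written in advance would remove both the ambiguity and any choice of interval after the result is known.

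Part of this stands. The sidedness is unstated, the arithmetic is right, and a hasty reader could be puzzled by a significant result beside an interval that includes zero.

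The rest does not carry. The reader is not left without a rule: the sentence just before the interval makes the p value the criterion. Nor does an interval including zero conflict with what the plan would conclude at p = 0.07 or 0.08, since all it claims is that such a result "would not yield a negative study but instead suggest that larger studies are worthy of pursuit". An interval from roughly -0.1 to 2.0 points is consistent with that modest claim. Choosing the interval late offers little room for manoeuvre, because the difference and its standard error fix every version of it.

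The alternatives also have a price. A one-sided bound drops the upper limit, which is useful when planning a later trial. A two-sided 80% interval keeps both limits at lower confidence. A two-sided 90% interval is a valid estimate with its stated coverage, and an estimation interval need not mirror the test.

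**Conclusion.** The observation is accurate, but it does not call for a change. If a one-sided 90% bound was intended, test and interval agree exactly. If a two-sided 90% interval was intended, it is a legitimate estimate that will include zero in about 11% of trials (about 13% of positive ones) under the plan's main scenario at 30 patients, while the p < 0.10 rule alone settles significance. On both readings the error rate, power, sample size, data and conclusion are unaffected.

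What remains is an unstated word in a reporting sentence. Analysts fill it as a matter of course by labelling the interval in the results table. Which interval to show is a fair trade-off between mirroring the test and describing the range of plausible effects.

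The frequencies rest on the plan's simulation inputs and an equal-variance t test with 15 patients per arm. The figures in pain points also rest on an SD of change that the plan does not state (1.71 simulated, 2.11 before truncation). The SE-unit results need only the 28 degrees of freedom.
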